8.2.1.3 Body Surface Area (BSA)

Measurement of psoriasis BSA involvement is estimated using the handprint method with the size of a subject's handprint (including fingers and thumb) representing 1% of BSA involved. The total BSA = 100% with breakdown by body region as follows:

- Head and neck = 10% (10 handprints),
- Upper extremities = 20% (20 handprints),
- Trunk including axillae and groin = 30% (30 handprints),
- Lower extremities including buttocks = 40% (40 handprints).

The Total BSA is the sum of each body region and is assessed at each visit and recorded in the eCOA system.

The product of BSA and sPGA will be calculated. At baseline, baseline BSA will be multiplied by baseline sPGA score. The derivation will be performed at each subsequent visit.

8.2.1.4 scalp specific Physician's Global Assessment (ss-PGA)

The scalp specific assessment will only be performed in subjects with scalp involvement. If there is evidence of scalp involvement, scalp lesions are evaluated in terms of clinical signs of redness, thickness, and scaliness and scored on the following 5-point ss-PGA scale:

0 = absence of disease, 1 = very mild disease, 2 = mild disease, 3 = moderate disease, 4 = severe disease.

The ss-PGA is assessed at each visit throughout the study in subjects that have evidence of scalp psoriasis at baseline. The score will be collected in the eCOA system.

Sponsor: Bristol-Myers Squibb
Protocol no: IM011065

8.2.1.6 Physician's Global Assessment-Fingernails (PGA-F)

In this assessment, fingernail psoriasis is evaluated. The PGA-F will be performed at baseline. If a subject shows evidence of psoriatic fingernail involvement, the assessment will be performed at each subsequent visit to assess severity and improvement over time. Only subjects with PGA-F at baseline will be assessed throughout the study. The overall condition of the fingernails is rated on a 5-point scale:

0 = clear, 1 = minimal, 2 = mild, 3 = moderate, and 4 = severe

The rating score will be collected in the eCOA system.

8.2.1.8 Palmoplantar PGA (pp-PGA)

[figure not shown]
This measure will be used for subjects with palmoplantar (finger and toe surfaces) involvement at baseline. Only subjects with baseline palmoplantar involvement will continue to have these

Sponsor: Bristol-Myers Squibb
Protocol no: IM011065

assessments at each subsequent visit throughout the study. The pp-PGA uses a 5-point (0-4) overall severity scale:

0 = clear; 1 = almost clear; 2 = mild; 3 = moderate; and 4 = severe.

Scores are collected at each visit and entered in the eCOA system.

8.2.2 Subject-Reported Assessments

8.2.2.1 Psoriasis Symptoms and Signs Diary (PSSD)

The PSSD is an 11-item subject-reported instrument that assesses severity of symptoms and subject-observed signs commonly associated in plaque psoriasis. It has been shown to be reliable and valid in measuring symptoms and signs of subjects with moderate-to-severe plaque psoriasis in the clinic and has strong psychometric properties in assessing treatment effects in clinical trials. The PSSD assesses severity of 5 symptoms (itch, pain, stinging, burning, skin tightness) and 6 subject-observed signs (skin dryness, cracking, scaling, shedding or flaking, redness, bleeding) using 0–10 numerical ratings. The severity of each item is rated on an 11-point numeric rating scale ranging from 0 (absent) to 10 (worst imaginable).

The following questions in the instrument are included in the symptom score: Q1, Q4, Q9, Q10, Q11

The following questions in the instrument are included in the sign score: Q2, Q3, Q5, Q6, Q7, Q8

Two versions of the PSSD were developed, one with a 24-hour recall period (PSSD-24h) and one with a 7-day recall period. The PSSD-24h will be administered daily in this trial to avoid recall bias

Sponsor: Bristol-Myers Squibb
Protocol no: IM011065

with a longer recall period. Individual scores to each question are collected daily in the PSSD. For visit PSSD scoring, the daily scores (with 24-h recall periods) over the prior 7 day will be used and the average score to each of the 11 questions will be used as the score at that visit. In case missing data arise during the 7 days prior to the visit, daily scores of at least 4 days out of the 7 can be used. If >3 scores are missing, the average score will be missing. Baseline PSSD score is calculated based on the daily diary collected data during the screening period. Baseline for each PSSD question will be calculated as the average value over the 7 days prior to the randomization visit. In the event of missing values in the 7 days prior to the randomization visit, daily scores from at least 4 days out of the 7 days can be used to calculate the average score. If > 3 daily scores in the last 7 days are missing for a particular question, then the baseline value for that question will be missing. If any questions are missing baseline after using the described rule, then the baseline value for the subscore using that question and the baseline value for the total score will be missing.

A symptom score will be derived by averaging the 5 questions included in the symptom score and multiplying by 10. To obtain a symptom score on a given day, responses to at least 2 of the 5 questions must be available. If 3 or more questions are missing, the symptom score is considered missing.

A sign score will be derived by averaging the 6 questions included in the sign score and multiplying by 10. Responses to at least 3 of the 6 questions must be available in order to obtain a sign score for a given day. If more than 3 questions are missing, the sign score is considered missing.

Both scores range from 0-100, where 0 representing the least severe symptom/sign and 100 the most severe. A total PSSD score with range 0-100 will be derived from taking the average of the symptom and sign scores.

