Chest Imaging (eg, Chest x-ray)	X	Chest imaging is required if not performed within 6 months of screening visit, copy of radiology report must be on file and reviewed by the investigator. Section 8.4.4 .
Neuropsychiatric Illness Assessment	X	Based on subject/family response, medical history/medical records, investigator judgment
PHQ-8	X	For establishing baseline depression severity
Suicidal Ideation and Behavior Assessment	X	Based on subject/family response, medical history/medical records, investigator judgment
eC-SSRS	X	eC-SSRS Assessment: Response of “Actual Suicide Attempt-Lifetime” or suicidal ideation (Severity of 4 or 5) or suicidal behavior will be exclusionary. Rescreening will not be allowed. Section 8.4.7
Monitor for SAEs	X	All SAEs must be collected from the date of subject’s written consent until 30 days post discontinuation of dosing or subject’s participation in the study.
Laboratory Tests		
Hematology	X	Complete Blood Count (CBC) with differential
Chemistry Panel	X	
Fasting Lipid Panel	X	Subjects are required to fast for at least 10 hours prior to collection.
Urinalysis	X	
Hemoglobin A1C	X	
TSH	X	If TSH above normal reference range, test free T4; if TSH below normal range, test free T4 & T3..
hs-CRP	X	
Serology	X	Includes HCV antibody, HBsAg, HBsAb, HBcAb, HBV DNA, and HIV antibodies.
TB Test	X	In accordance with QuantiFERON-TB (details described in Section 8.4.4).

Table 1: Screening Procedural Outline (IM011065)

Procedure	Screening V1	Notes
Pregnancy Test (serum)	X	For WOCBP only
FSH	X	To confirm menopausal status (see APPENDIX 4)
Clinical Efficacy/Health Outcomes		
sPGA	X	
PASI	X	
BSA	X	
PASE Questionnaire	X	For subjects with peripheral joint complaints to screen for presence of psoriatic arthritis
PSSD	X	All consented subjects will be given a diary device at the Screening Visit and will begin recording psoriasis signs and symptoms on a daily basis in the diary device. Subjects who are not randomized will stop recording and return their diary device to the site. Subjects who are randomized will continue recording their psoriasis signs and symptoms on a daily basis in the diary device through Week 52.

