6.1.2 Key Secondary Endpoints

Analysis Model

CMH tests will be used to compare response rates between BMS-986165 6mg QD and placebo. The following stratification factors from IRT are included in the model: country (mainland China, non-mainland China) and prior biologic use (yes/no). The odds ratio (ratio of odds in BMS-986165 6 mg QD group to the odds in the placebo group) and the corresponding 2-sided 95%

Sponsor: Bristol-Myers Squibb
Protocol no: IM011065

CIs and p-values will be reported. Additionally, treatment differences in proportions and the 95% CI for the treatment difference will be provided.

Imputation Methodology for Week 16 Endpoints

NRI will be used for key secondary efficacy endpoints for subjects who:

- Discontinue treatment or study prior to Week 16
- Have missing Week 16 endpoint data for any reason

Imputation Methodology for Week 52 Endpoints

The key secondary endpoints included in this analysis are the following:

- sPGA 0/1 response with at least a 2-point improvement from baseline at Week 52 and at Week 16
- PASI 75 response at Week 52 and at Week 16

Subjects must meet response criteria at both Weeks 16 and 52 in order to be considered a responder. Those who do not meet response criteria at both weeks will be considered a nonresponder.

NRI will be used for key secondary endpoints for subjects who:

- Discontinue treatment or study prior to Week 52
- Have missing Week 52 data

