8.0 Conventions

8.1 General Definitions

The following data definitions and handling conventions will be used for general analysis:

Sponsor: Bristol-Myers Squibb
Protocol no: IM011065

Term	Definition
Study Day	
For dates prior to the first dose date, assessment date – first dose date
 
For dates on or after the first dose date, assessment date – first dose date + 1 day

Baseline	
Unless otherwise stated, Baseline is defined as the last measurement at the randomization visit (Week 0). If the measurement on Day 1 is missing, then a prior measurement during the screening period may be used as baseline. Baseline assessments must be performed per protocol and standard of care assessments may not be used for baseline.
 
Baseline for each PSSD question will be calculated as the average value over the 7 days prior to the randomization visit. In the event of missing values in the 7 days prior to the randomization visit, daily scores from at least 4 days out of the 7 days can be used to calculate the average score. If > 3 daily scores in the last 7 days are missing for a particular question, then the baseline value for that question will be missing. If any questions are missing baseline after using the described rule, then the baseline value for the subscore using that question and the baseline value for the total score will be missing.

Change from Baseline	Change from baseline is defined as (value at post-baseline visit – value at baseline).
Change from baseline to the maximum post-baseline value or change from baseline to the worst post-baseline value	The maximum/worst post-baseline value is defined as highest/worst observed post-baseline value. The change from baseline is calculated using this maximum/worst value - baseline value.
Concomitant and Prior Medication	
Prior medications are defined as medications that started prior to first study treatment, but no longer being taken at the time of the study. i.e. start and stop prior to the first study treatment.
 
Concomitant medications are defined as any medications ongoing at the start of study treatment or with a start date on or after the first dose date and prior to the last dose date.
 
Post study medications are defined as medications that started after the last dose of study treatment.

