8.5 Day Ranges for Analysis Visits

Below are the day ranges for the analysis visit definitions. If more than one visit occurs within an analysis visit, then the visit that is closest to the target date should be used for analysis.

Period	Week	Target Day	Day Range
Baseline			Screening, 1
Period 1			
	Week 1	8	2, 11
	Week 2	15	12, 18
	Week 4	29	19, 43
	Week 8	57	44, 71
	Week 12	85	72, 99
	Week 16	113	100, Week 16 drug dispense date (if available) or use 127 if missing
Period 2			
	Week 20	141	1 st day after Week 16 drug dispense date, 155
	Week 24	169	156, 183
	Week 28	197	184, 211
	Week 32	225	212, 239
	Week 36	253	240, 267
	Week 40	281	268, 295
	Week 44	309	296, 323
	Week 48	337	324, 351
	Week 52	365	352, last visit date prior to Safety Follow-up

Sponsor: Bristol-Myers Squibb
Protocol no: IM011065

Period		
Week	Target Day	Day Range
Safety Follow-up	393	Safety Follow-up visit*

* The Safety Follow-up visit is identified from the SDTM visit label, and no windowing is applied for the creation of this analysis visit. Subjects who continue into the extension study are not expected to complete a safety follow-up.

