Appendix 2 Summary of Efficacy Assessments

Assessment	Outcome Measure	Endpoint	Comparison	Analyses
sPGA (Sec 8.2.1.1)	sPGA 0/1 with at least 2 point improvement from baseline	W16	BMS vs. PBO	CMH, sensitivity analyses including tipping point analysis, multiple imputation (Sec 6.1.1.1-3)
		Baseline->W16 over time	BMS vs. PBO	Binary GEE and CMH by Week (Sec 6.1.5.1)
	sPGA 0	W16	BMS vs. PBO	CMH (Sec 6.1.2.1)
		Baseline->W16 over time	BMS vs. PBO	CMH by Week (Sec 6.1.5.1)
PASI (Sec 8.2.1.2)	PASI 75	W16	BMS vs. PBO	CMH, sensitivity analyses including tipping point analysis, multiple imputation (Sec 6.1.1.1-3)
		Baseline->Week 16 over time	BMS vs. PBO	Binary GEE and CMH by Week (Sec 6.1.5.1)
	PASI 90	W16	BMS vs. PBO	CMH (Sec 6.1.2.1)
		Baseline->W16 over time	BMS vs. PBO	CMH by Week (Sec 6.1.5.1)
	PASI 100	W16	BMS vs. PBO	CMH (Sec 6.1.2.1)
		Baseline->W16 over time	BMS vs. PBO	CMH by Week (Sec 6.1.5.1)
ss-PGA (Sec 8.2.1.4)	ss-PGA 0/1 among subjects with a baseline ss-PGA ≥ 3	W16	BMS vs. PBO	CMH (Sec 6.1.2.1)
		Baseline->W16 over time	BMS vs. PBO	CMH by Week (Sec 6.1.5.1)

Sponsor: Bristol-Myers Squibb
Protocol no: IM011065

PGA-F (Sec 8.2.1.6)	PGA-F 0/1 among subjects with a baseline PGA-F score ≥ 3	W16 Baseline->W16 over time	BMS vs. PBO	CMH (Sec 6.1.2.1) CMH by Week (Sec 6.1.5.1)
pp-PGA (Sec 8.2.1.8)	pp-PGA 0/1 among subjects with a baseline pp-PGA ≥ 3	W16 Baseline->W16 over time	BMS vs. PBO	CMH (Sec 6.1.2.1) CMH by Week (Sec 6.1.5.1)
PSSD / Symptom Score (Sec 8.2.2.1)	PSSD/Symptom 0 among subjects with baseline PSSD/symptom score ≥ 1	W16 Baseline->W16 over time	BMS vs. PBO	CMH (Sec 6.1.2.1) CMH by Week (Sec 6.1.5.1)

Sponsor: Bristol-Myers Squibb
Protocol no: IM011065

DLQI (Sec 8.2.2.2)	DLQI 0/1 among subjects with a baseline DLQI score ≥ 2	W16 Baseline->W16 over time	BMS vs. PBO	CMH (Sec 6.1.2.1) CMH by Week (Sec 6.1.5.1)
-----------------------	--	--------------------------------	-------------	--

Sponsor: Bristol-Myers Squibb
Protocol no: IM011065

PASE (Sec 8.2.2.8)	PASE	Screening only		No Analysis

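### PSSD visit scores have no lower limit at first dose, so early Week 1 visits average in baseline days; and the SAP does not say how to score the diary if the Week 16 visit is missed

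*SAP*

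**What the plan says.** The PSSD is a daily home diary, and its entries do not depend on site visits. Protocol 1.3, Table 1 states: "Subjects who are randomized will continue recording their psoriasis signs and symptoms on a daily basis in the diary device through Week 52".

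Scoring, however, is tied to visits. SAP 8.2.2.1 says "For visit PSSD scoring, the daily scores (with 24-h recall periods) over the prior 7 day will be used", averaged question by question. When entries are missing, "daily scores of at least 4 days out of the 7 can be used". Nothing in that section requires the days to fall after first dose. SAP 8.1 sets the comparison point: "Baseline for each PSSD question will be calculated as the average value over the 7 days prior to the randomization visit".

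Study days are numbered without a Day 0. For dates from first dose on, SAP 8.1 gives "For dates on or after the first dose date, assessment date – first dose date + 1 day"; earlier dates take the plain difference, so the day before first dose is Day -1.

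Protocol 1.3, Table 2 places the Week 1 visit at Day 8 with a tolerance of 3 days either way. SAP 8.5 accepts Days 2 to 11 as Week 1. It accepts Day 100 up to the Week 16 dispensing date as Week 16, or up to Day 127 if that date is missing. These ranges select visits rather than diary days: "If more than one visit occurs within an analysis visit, then the visit that is closest to the target date should be used for analysis".

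A PSSD symptom score of 0, among subjects with a baseline score of at least 1, is a key secondary endpoint at Week 16 (SAP 4.1.2.1 and 6.1.3). SAP Appendix 2 also lists it over time from baseline to Week 16, with a CMH test by week. SAP 6.1.3 makes no multiplicity adjustment at other time points. SAP 6.1.2 applies non-responder imputation (NRI) to subjects who stop treatment or study before Week 16, and also under the condition "Have missing Week 16 endpoint data for any reason".

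**The concern.** A seven-day look-back from a visit that may take place fewer than seven days after first dose must reach into the pre-treatment period. Those days already form part of the baseline, so a value labelled Week 1 would partly repeat the baseline. For an outcome that requires a score of exactly 0, this is more than dilution: a single symptomatic pre-dose entry in the average makes response impossible, whatever happened after dosing.

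Tying the score to a visit raises a second question. The diary can be complete for the week before Day 113 even if the subject does not come to the site. If the score exists only when a visit exists, an observed patient-reported outcome would be replaced by an imputed failure, and at Week 16 that touches an endpoint in the testing hierarchy.

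**Working it through.** There is no figure in the plan to reproduce. The check is a count of diary days.

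**Inputs.** Look-back of 7 days and a minimum of 4 (SAP 8.2.2.1). Baseline Days -7 to -1 and no Day 0 (SAP 8.1). Week 1 visit on Days 8 - 3 = 5 to 8 + 3 = 11 (Protocol Table 2). Assumption: first dose is taken on the day of randomization, Day 1.

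**Count.** If the seven days end the day before a visit on Day V, then V - 1 of them lie on or after Day 1. The pre-dose count is 7 - (V - 1) = 8 - V for V up to 8, and 0 afterwards. If the visit day is one of the seven, the count is 7 - V for V up to 7. The text does not settle which is meant.

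| Week 1 visit | Seven days used (visit day excluded) | Pre-dose days | Pre-dose days if visit day included |
|---|---|---|---|
| Day 5 | -3 to 4 | 3 | 2 |
| Day 6 | -2 to 5 | 2 | 1 |
| Day 7 | -1 to 6 | 1 | 0 |
| Day 8 | 1 to 7 | 0 | 0 |
| Days 9-11 | all after Day 1 | 0 | 0 |

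Every pre-dose day in the table lies within Days -7 to -1, so it is also a baseline day. The Day 1 entry is counted here as post-dose, although its 24-hour recall reaches back before first dose.

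**With the 4-of-7 minimum.** A Day 5 visit with no entries on Days 2, 3 and 4 still gets a score, from Days -3, -2, -1 and 1. That is 3 pre-dose days of 4, or 75%.

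**Effect on a score of 0.** Items run from 0 to 10, and the symptom score is 10 times their mean. A mean of non-negative values is 0 only if every value used is 0. The endpoint includes only subjects with a baseline symptom score of at least 1, so each has some non-zero entry in Days -7 to -1. If one falls on a pre-dose day used in the Week 1 average, the subject cannot respond. The direction is toward non-response in both arms. Its size cannot be computed, because the documents give neither the spread of visit days nor Week 1 response rates.

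**Later visits.** The earliest Week 2 visit (Day 12) uses Days 5 to 11. Week 16 visits within the protocol tolerance (Days 110 to 116) use days between 103 and 115. Neither reaches the baseline.

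**Week 16 without a visit.** Three provisions have to be read together: the score is defined at a visit (SAP 8.2.2.1), the Week 16 range selects a visit (SAP 8.5), and NRI covers any missing Week 16 value (SAP 6.1.2). With no visit between Day 100 and Day 127 there is no anchor, hence no score, hence non-response, even if Days 106 to 112 are complete. The remark in SAP 8.2 that eCOA prompting prevents missing assessments concerns attended visits.

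**The case against.** Much can be said on the other side, and most of it limits the point rather than removing it.

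- **No confirmatory result is touched by the overlap.** A reader might infer that the key secondary PSSD endpoint is biased. It is not: it is defined at Week 16, far from the baseline days, and the Week 1 comparison carries only nominal p-values.
- **A Week 1 PSSD analysis is itself an inference.** It follows from the by-week entry in SAP Appendix 2. The PSSD row in Protocol Table 2 shows no visit marks in the text available, and SAP 6.1.5.1, to which the appendix refers, is not shown. This stands as a caveat.
- **The share of pre-dose days is not a shrinkage of the treatment effect.** A reader might take 3 of 7 days as a proportional loss. That would need a mean score and a full, constant effect from Day 1. The by-week analysis shown is binary, and few subjects may reach 0 at Week 1 under any rule.
- **Visits on Days 2 to 4 are outside the protocol tolerance.** SAP 8.5 would accept them, but the point does not need them; Days 5 to 7 are allowed by the protocol.
- **The SAP never says a complete diary is discarded.** A reader might state that as a rule of the plan, but the text is silent. The Day 100 to 127 range lets another visit serve as anchor. Kits hold a 4-week supply (Protocol 6.2), so a subject continuing treatment would normally attend. SAP 6.5.1, on COVID-19 and efficacy endpoints, is listed in the contents but not shown, and may deal with missed visits.

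What remains is that the scoring rule, as written, has no lower limit at first dose, and that the text available gives no anchor when the Week 16 visit is absent.

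**Conclusion.** The point holds as a minor gap in the scoring rule. For a Week 1 visit on Day 5, 6 or 7, the PSSD score includes 3, 2 or 1 pre-dose days that also form the baseline (2, 1 or 0 if the visit day counts). Any Week 1 by-week result for a score of 0 is biased toward non-response for those visits. This rests on first dose being on the randomization day and on Week 1 being an analysed PSSD time point.

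On the missed Week 16 visit, the supported statement is conditional: a literal reading makes a subject still on treatment, with a complete diary but no visit in the window, a non-responder. The number affected is unknown and probably small. A subject's result would change only if the baseline score was at least 1 and the diary score would have been 0. The documents give no rate of missed visits, so no count is offered.

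**What to change.** Add two sentences to SAP 8.2.2.1.

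1. Post-baseline PSSD averages use only diary entries dated after Study Day 1, with the 4-of-7 minimum kept; if fewer than 4 such days precede the Week 1 visit, diary Days 2 to 8 are used. With the visit day excluded, a Day 5 visit has 3 usable days (2 to 4) and takes the fallback; Day 6 has 4, Day 7 has 5, Day 8 has 6, and later visits have 7. Leaving out Day 1 also removes the entry whose 24-hour recall is largely pre-dose. The same sentence should say whether the visit day counts.
2. If there is no visit in the Week 16 window and treatment continues, the 7 diary days before target Day 113 (Days 106 to 112) are scored, under the same minimum, before NRI is applied.

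The cost is a small programming change, and no new data are needed. Week 16 scores of attending subjects do not change. The drawback is that the Days 2 to 8 fallback uses some entries made after an early visit: for a Day 5 visit, those of the following days up to Day 8.
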